3.5.6 Patient-reported Experience

Participants will be asked to respond in writing (free text) to 3 open-ended questions about their experience with AD and their study intervention. The assessment will be conducted during the site visits specified in the SoA (CSP Table 3), using a provisioned tablet to access the secure web form.

Data from the free text collection will be used for exploratory descriptive analysis using machine learning technologies. Due to the qualitative nature of the data and the analysis, the results will be presented in a separate report (not in the CSR) and the data will not be entered into the study database.

The Patient-reported Experience will be analyzed separately and not form part of this SAP.

3.5.7 Body Surface Area Involvement of Atopic Dermatitis

Body surface area affected by AD will be assessed for each section of the body using the Palmar method with rule of nine. The possible highest score for each region is: head and neck [9%], anterior trunk [18%], back [18%], upper limbs [18%], lower limbs [36%], and genitals [1%], and will be reported as a percentage of all major body sections summed together. Participants will undergo this assessment at time points according to the SOA (CSP Table 3). The body surface area affected scoring will also be calculated on the electronic device that is supplied to the site. The ePRO does not allow for questions to be unanswered, so no consideration is required for missing data.

Intercurrent events will be considered as described above in Section Intercurrent Events (Section 3.1.5) Intercurrent events will be considered for analyses and descriptive summaries.

3.5.8 European Quality of Life-5 Dimensions (EQ-5D-5L)

The European Quality of Life-5 Dimensions (EQ-5D-5L) questionnaire will be assessed at on-site Visits 1, 2, 6, 7, 12, 16, and IPD visit, and at home every 28 ± 3 days after Visit 2 until Visit 6 is confirmed, on the electronic device supplied to the participants.

The EQ-5D-5L assesses 5 dimensions: mobility, self-care, usual activities, pain/discomfort, and anxiety/depression. Each dimension has 5 response options (no problems, slight problems, moderate problems, severe problems, and extreme problems) that reflect increasing levels of difficulty.

The participant will be asked to indicate his/her current health state by selecting the most appropriate level in each of the 5 dimensions. The questionnaire also includes a VAS, where the participant will be asked to rate current health status on a scale of 0 to 100, with 0 being the worst imaginable health state.

The European Quality of Life-5 Dimensions (EQ-5D-5L) will be analyzed separately and not form part of this SAP.

CCI

CCI

3.5.11 Biomarkers

CCI

3.5.12 Clinical skin photography

Clinical skin photography is a method to capture and document images of the skin. To evaluate alternative methods of clinical assessments, skin photography will be used in this study. Full body photographs will be taken as outlined in the photography manual and according to the SoA (CSP Table 3). At visits when clinical skin photography is to be performed and assessed before the Investigator sees the participant for the study visit, the photographs should be taken by a trained site personnel and not by the Investigator performing efficacy assessments on the participant. The site Investigator will then review the photographs and perform the clinical efficacy assessments (IGA, EASI, SCORAD, and BSA) based on review of the photographs. The Investigator photograph assessment will be recorded in the electronic case report form (eCRF). The same site Investigator should then see the participant and perform the usual in-person visit assessments including the in-person assessment of efficacy parameters, and document the data. The first assessments (based on skin photography) should not be altered even if differences are observed after assessing the participant in person. The final in-person Investigator assessment documented should reflect

the Investigator's overall clinical judgment. Photographic equipment will be provided to the sites.

The clinical efficacy assessments (IGA, EASI, SCORAD, and BSA) are described for primary and secondary endpoints in Sections 3.2 and 3.3 above. For these exploratory analyses of agreement between the in person and photograph assessment, the total scores or matching sub-scores will be used.

All available data will be included, regardless of intercurrent events like taking rescue medication or withdrawal from study.

The photographic assessment results will be examined against the in-person assessment results at Week 16 analyses.

4 ANALYSIS METHODS

The primary DBL is targeted to occur when all participants have completed the 16-week placebo-controlled treatment period. The final DBL will occur when all participants have completed the 52-week treatment period and the Week 60 follow-up visit and/or the IP discontinuation (IPD) /EOT visit.

All data will be included in the analyses, regardless of whether IP was prematurely discontinued or delayed, and irrespective of protocol adherence, unless the participant withdrew consent to further study participation.

All personnel involved in the analyses of the study will remain blinded until the primary DBL and protocol deviations are identified.

The CSR will be based on the final DBL.

4.1 General principles

The primary efficacy analyses will be based on the double-blind, 16-week placebo-controlled treatment period. Final analyses will be based on Week 52 end of study reporting. Efficacy endpoints will be analyzed using the FAS, the analysis of safety endpoints will be based on the safety analysis set. Analysis sets are defined in Section 2.2.

For the primary Week 16 analyses of binary endpoints, assessments after the use of rescue medication from Day 29 onwards will be considered as non-responders from the point of the rescue medication onwards. Any missing visits (including data after withdrawal of study at any time) will also be considered as non-responders, as described in Table 11 below.

For the primary Week 16 analyses of continuous repeated measures endpoints, any data after the use of rescue medication from Day 29 onwards or after withdrawal from study at any time will be treated as missing and the MMRM analyses fitted on the remaining available data.

For Week 52 analyses, for participants on benralizumab from randomization, rescue therapy use from Day 29 onwards will result in the participants being considered non-responders from the point of rescue use onwards. However, for participants who started on placebo and switched to benralizumab in the extension phase, rescue therapy users will only be considered as non-responders for the Week 52 analyses if it was taken from Day 141 (ie 29 days after first dose of benralizumab) onwards. Participants after withdrawal of study at any time will be considered as non-responders. Similarly, for change from baseline analyses, those intercurrent events will be considered as missing data.

Summary data will be presented in tabular format by treatment group. Categorical data will be summarized using frequencies and percentages, where the denominator for calculation is the underlying analysis set population unless otherwise stated. For efficacy reporting, the proportions of responders presented over time will include a number in analysis row to show the number of participants who have had the opportunity to reach each timepoint by the primary analysis based on their randomisation date, and this number in analysis will be used as the denominator for each visit.

Continuous data will be summarized with descriptive statistics of number of available observations, mean, standard deviation (SD), median, minimum and maximum, and quartiles where more appropriate. Mean and median will be reported to one decimal place more than the data recorded, the SD to one decimal place more than the mean, other items to the precision recorded (maximum rounded to 4 decimal places). Data listings will be sorted by treatment and participant number.

All point estimates will be presented together with 95% confidence intervals (CIs) as measures of precision and nominal 2-sided p-values, rounded to 4 decimal places.

For Week 16 analyses, all data over the entire 16-week placebo-controlled treatment period (or last dose in placebo-controlled period + 30 days for those who do not enter the extension period) will be presented in summaries and data listings (see Section 2.1).

For Week 52 end of study reporting, all data over the entire 52-week treatment period (and Week 60 follow-up visit and/or IPD/EOT visit) will be presented in summaries and data listings (see Section 2.1).

Analyses for the first 16 weeks will compare the two initial treatment groups, benralizumab 30 mg Q4W Total and placebo Q4W. Summaries will also display the randomized treatment sequences (benralizumab 30 mg Q4W/Q4W, benralizumab 30 mg Q4W/Q8W).

Analyses for the Week 52 end of study reporting will be presented by the 3 randomized treatment sequences (benralizumab 30 mg Q4W, benralizumab 30 mg Q8W and placebo/benralizumab), as noted in Section 1.1.1. Summaries will also display the initial benralizumab 30 mg Q4W Total group. For efficacy analyses, the Q4W versus Q8W dosing regimen will be statistically compared for participants originally randomized to benralizumab 30 mg Q4W initial dose, with all data (including placebo/benralizumab group) included in the model.

Additionally, a small number of key efficacy and safety tables will also be presented for data in the extension period alone to explore where a direct comparison of Q4W versus Q8W dosing can be made for participants previously receiving benralizumab, and to summarize time on benralizumab alone for participants previously receiving placebo. Adverse events will be presented for each period separately and only overall for key tables.

The data analyses will be conducted using the SAS® System (SAS Institute Inc., Cary, NC). All SAS® programs used to generate analytical results will be developed and validated according to AstraZeneca SAS® programming standards and validation procedures.

Table 11 Primary and key secondary efficacy and main safety estimands

Statistical Category	Estimand ^a				Section
	Treatment Condition ^a	Endpoint (Population)	Intercurrent Event Strategy ^a	Population Level Summary ^a (Analysis)	
Primary Objective: To compare the clinical efficacy of benralizumab 30 mg with placebo in patients with AD despite treatment with topical medications					
Primary	Treatment with benralizumab versus placebo, regardless of compliance, where rescue from Day 29 indicates treatment failure	
 • A binary response giving the proportion of patients with an IGA 0/1 and a decrease in IGA of ≥ 2 points at Week 16 relative to baseline (FAS) 	
 • All data up to Week 16 will be included • Treatment discontinuation – treatment policy • Rescue medication from Day 29 onwards – non-responders • Withdrawal from study – non-responders 	
 • Odds ratio, with corresponding 95% CIs (logistic regression) 	4.2.6.1
Key secondary objective: To compare the effect of benralizumab with placebo on supportive measures of clinical efficacy in patients with AD despite treatment with topical medications					
Key secondary	Treatment with benralizumab versus placebo, regardless of compliance, where rescue from Day 29 indicates treatment failure	
 • Proportion of patients with skin clearance (EASI-75) at Week 16 (FAS) • Proportion of patients with an improvement of ≥ 4 or more points in peak pruritus weekly score at Week 16 (FAS) • Proportion of patients with skin clearance (EASI-90) at Week 16 (FAS) 	
 • All data up to Week 16 will be included • Treatment discontinuation – treatment policy • Rescue medication from Day 29 onwards – non-responders • Withdrawal from study – non-responders 	
 • Odds ratio, with corresponding 95% CIs (logistic regression) 	4.2.7.1, 4.2.7.2
Safety Objective: To compare the safety and tolerability of benralizumab with placebo in patients with AD despite treatment with topical medications					
Safety	Treatment with benralizumab versus placebo, regardless of rescue medication	
 • Presence of TEAEs through EOT (safety) • Presence of serious TEAEs through EOT (safety) 	Remained adherent to intervention (on-treatment)	
 • Categorical descriptive 	4.2.8

^a All estimand attributes explicitly identified for primary and key secondary estimands only.

4.1.1 Testing strategy to account for multiplicity considerations

A hierarchical testing procedure will be used to control the overall Type I error rate at 5% across the primary and key secondary endpoints

Hypothesis testing for the primary and key secondary endpoints (Sections [4.2.6.1](#), [4.2.7.1](#), [4.2.7.2](#)) will be sequentially in the following order and based on a 2-sided test and carried out using a 5% significance level:

- 1 Proportion of participants with IGA 0/1 (ie, clear or almost clear) and a decrease in IGA of 2 or more points at Week 16, relative to baseline;
- 2 Proportion of participants with EASI-75 at Week 16;
- 3 Proportion of participants with an improvement of 4 or more points in peak pruritus weekly score at Week 16, relative to baseline;
- 4 Proportion of participants with EASI-90 at Week 16.

If the treatment comparison for (1) is statistically significant, testing will proceed to (2), and so on through the testing hierarchy. If, at any point in this hierarchy, a null hypothesis cannot be rejected at the 5% significance level in favor of benralizumab, further testing will stop, and no subsequent null hypotheses will be rejected.

4.2 Analysis methods

4.2.1 Participant disposition

Participant disposition will be summarized using the all participants analysis set. The total number of participants will be summarized for the following groups: those who enrolled, those who entered run-in, and those who were not randomized (and reason). The number and percentage of participants within each treatment group will be presented by the following categories: (a) for 16-week placebo-controlled treatment period: randomized, received treatment with IP, did not receive treatment with IP (and reason), completed treatment period with IP, discontinued treatment with IP (and reason), discontinued treatment with IP but completed study follow-up, completed treatment, and withdrawn from study (and reason), (b) for extension period: entering, not entering (and reason) , completed treatment period with IP, discontinued treatment with IP (and reason), discontinued treatment with IP but completed study follow-up, completed treatment, and withdrawn from study (and reason).

Screen failure information will be listed for the all participants analysis set.

For participants in the FAS, the number of participants remaining on treatment, participants discontinued IP but still in study follow-up, and participants who withdraw from the study will be summarized by treatment group and scheduled visit.

The number of participants randomized by country and center will also be summarized by treatment group in the FAS.

Disposition summaries will be presented for both, the 16-week placebo-controlled treatment period and the Week 52 end of study reporting.

4.2.2 Demography data and participant characteristics

Demography and baseline characteristics will be summarized by treatment group and overall in the FAS, using frequency and percentages (for categorical variables) and descriptive statistics of n, mean, standard deviation, median, minimum, and maximum, and where appropriate 1st quartile (Q1) and 3rd quartile (Q3) (for continuous variables). If there are major differences in the number of participants between the FAS and safety analysis set, these summaries will be repeated for the safety analysis set.

Age will be derived from the date of informed consent and date of birth, rounded down to the nearest integer. For participants in countries where date of birth is not recorded, the age as recorded in the eCRF will be used.

Various baseline characteristics will also be summarized, including participant characteristics (screening age (as continuous and categorical variable (≥ 12 to < 18 years/ ≥ 18 years)), weight, height, BMI, ethnicity, race, screening blood eosinophils (< 300 cells/ μL / ≥ 300 cells/ μL)). Medical and surgical histories will be summarized separately for past and current conditions by MedDRA Preferred Term (PT) within MedDRA System Organ Class (SOC). History of AD and age (years) at first appearance and diagnosis of AD and time since first appearance and diagnosis (years) will be summarized separately.

The handling of partial/missing dates for age (years) at/time since first appearance/diagnosis of AD is as follows, to allow for durations to be presented: If the day of date of appearance/diagnosis is missing it will be set to the first day of the month that the appearance/diagnosis occurred. If the date of appearance/diagnosis is missing both the day and month, and the year of appearance/diagnosis is in the same year as the year of birth, then set the date to be equal to date of birth (if both the day and month of birth are missing then set to January 1 of the year of birth; if the day of birth is missing then set to the first day of the month of birth); otherwise the date will be set to January 1 of the year of diagnosis.

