4.2.6.2 Subgroup analyses for the primary outcome variable

To explore the uniformity of the detected overall treatment effect on the primary efficacy variable, subgroup analyses and statistical modelling including testing for interaction between treatment and covariates will be performed for the following factors:

- Region (Europe, North America, Rest of World)
- Gender (male, female)
- Age group categories (< 18 years, ≥ 18 – 35 years, ≥ 35 years) at screening from eCRF
- Age group categories (< 21 years, ≥ 21 – 35 years, ≥ 35 years) at screening from eCRF
- Blood eosinophils (< 300 cells/μL, ≥ 300 cells/μL) at screening from central laboratory results
- BMI ($\leq 30 \text{ kg/m}^2$, $> 30 \text{ kg/m}^2$)
- Race (White, Asian, Other)
- Duration of AD at enrolment (< median, ≥ median; calculated on FAS)
- Age at onset of AD (< 18 years, ≥ 18 years; if sufficient data: < 12 years, ≥12 – 18 years, ≥ 18 years)
- Baseline IGA score (3, ≥ 4)
- Baseline EASI (< median, ≥ median)
- Previous biologic use (yes, no; if sufficient data: responded to, failed, naïve) at screening from eCRF
- Previous immunosuppressant (yes, no; if sufficient data: responded to, failed, naïve) at screening from eCRF
- Co-morbid asthma (yes, no) at screening from eCRF
- IgE (< median, ≥ median) from central laboratory results; calculated on FAS
- Staph aureus (lesional) (yes, no)
- Staph aureus(non-lesional) (yes, no)
- Aeroallergens (yes, no) at screening from eCRF
- Food allergies (yes, no) at screening from eCRF

For each of the subgroup factors in turn, a separate logistic regression model will be fitted using the same model terms as used for the primary analysis (described in Section 4.2.6.1),

with additional terms for the subgroup main effect (unless the subgroup main effect is already included) and the treatment by subgroup interaction. If any model does not converge, respective sub-groups may be collapsed appropriately.

Similar outputs will be presented for each subgroup as for the primary analysis. The p-value for the interaction term by each treatment group will be presented in the analysis summary tables and forest plots will present the odds ratios with confidence intervals for each level of the subgroups.

It is important to note that the study has not been designed or powered to assess efficacy within any of these pre-defined subgroups (except for strata of age and eosinophils), and as such these analyses are considered as exploratory.

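### The last branch of the partial-date rule for AD history names only the diagnosis year, so a year-only first-appearance date, if programmed as written, can be placed too late

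*SAP*

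**What the plan says.** Section 4.2.2 treats first appearance and diagnosis as distinct variables: "age (years) at first appearance and diagnosis of AD and time since first appearance and diagnosis (years) will be summarized separately". It then gives a single imputation rule for both, introduced by "The handling of partial/missing dates for age (years) at/time since first appearance/diagnosis of AD is as follows". The rule has three branches.

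- Day missing: "it will be set to the first day of the month that the appearance/diagnosis occurred".
- Day and month missing ("If the date of appearance/diagnosis is missing both the day and month"), in the birth year: if "the year of appearance/diagnosis is in the same year as the year of birth, then set the date to be equal to date of birth".
- Day and month missing, any other year: "otherwise the date will be set to January 1 of the year of diagnosis".

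Section 4.2.6.2 uses two variables of this kind as subgroup factors for the primary endpoint: "Age at onset of AD (< 18 years, ≥ 18 years; if sufficient data" there is a further split at 12 and 18 years, and "Duration of AD at enrolment (< median, ≥ median; calculated on FAS". It does not say whether duration starts at first appearance or at diagnosis. It calls the subgroup analyses exploratory.

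**The concern.** The first two branches refer to appearance and diagnosis together, so each date is completed from its own month or tested against its own year. Only the last branch names diagnosis alone. Read literally, it discards a recorded year of first appearance and substitutes the year of another event. The SAP gives no reason for doing so, and the effect works against its own decision to report the two dates as separate variables.

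Diagnosis does not normally precede first appearance, so the error would run in one direction, towards later onset and shorter time since onset. It would also depend on how precisely onset was recalled, because a complete date, or one missing only the day, keeps its own year. At stake are the baseline summaries of age at and time since first appearance, the age-at-onset subgroup and possibly the duration subgroup.

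**Working it through.** The SAP states no figure on this point, so there is none to reproduce. The check is date arithmetic on the rule.

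**General result.** Let appearance fall in calendar year a and diagnosis in year a + g, with appearance known only to the year and a not the birth year.

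- As written: imputed appearance is 1 January of a + g. The true date lies between 1 January and 31 December of a, so age at onset is overstated by between about g − 1 and g years.
- Own-year reading: imputed appearance is 1 January of a. Age at onset is understated by less than 1 year.
- If g = 0 the two readings agree.

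**Worked records.** These dates are assumed, not taken from the SAP: birth 15 June 1990, consent 1 June 2021. Age at onset = (imputed date − birth date) / 365.25.

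| Appearance | Diagnosis | As written | Own year | Possible true age |
|---|---|---|---|---|
| 1990 (birth year) | 1998 | 0.00 | 0.00 | 0 to 0.54 |
| 2000 | 2000 | 9.55 | 9.55 | 9.55 to 10.55 |
| 2000 | 2001 | 10.55 | 9.55 | 9.55 to 10.55 |
| 2000 | 2005 | 14.55 | 9.55 | 9.55 to 10.55 |
| 2001 | 2003 | 12.55 | 10.55 | 10.55 to 11.55 |
| 2007 | 2009 | 18.55 | 16.55 | 16.55 to 17.54 |

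The first two rows show no effect of the last branch. In the fourth, the overstatement is 14.55 − 10.55 = 4.00 to 14.55 − 9.55 = 5.00 years, and time since first appearance at consent is 16.41 years as written against 21.42 under the own-year reading. The fifth row crosses the 12-year cut and the sixth the 18-year cut.

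**Illustration of scale.** The SAP reports neither how many dates are year-only nor the delay to diagnosis, so every input here is an assumption:

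- age at screening uniform from 12 to 60 years;
- onset in the first two years of life for half of participants, and uniform between birth and current age for the rest;
- exponential delay with mean 0 to 5 years, diagnosis no later than screening;
- 25% to 100% of onset dates year-only;
- duration counted from first appearance.

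| Share of participants misclassified | As written | Own year |
|---|---|---|
| 18-year onset cut | 0.2% to 6.4% | 0.2% to 0.6% |
| Median of duration | 0.1% to 6.6% | 0.1% to 0.4% |

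The low end of the as-written range, with no delay, is the same as under the own-year reading. The table shows how strongly the result depends on the assumptions; it does not estimate what happens in this trial.

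**Neighbouring gap.** The missing-day branch has no guard at birth. A participant born on 15 June with onset recorded as that same June gets 1 June, 14 days before birth. The birth-year guard covers only dates missing both day and month.

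**The case against.** The strongest reply is that this is a slip of wording. The final clause continues a sentence about the appearance or diagnosis date, the branch condition tests that date's own year, and no other branch borrows from the other event. The literal reading also fails for a year-only appearance with no recorded diagnosis year, since it leaves nothing to impute. A programmer may well code the intended meaning, and then the bias disappears. This stands as an account of the cause. It does not remove the need to correct the text: following the approved SAP gives a wrong date, and silently correcting it departs from the SAP.

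The harm is also conditional. It needs literal programming, an onset date known only to the year, onset outside the birth year, and diagnosis in a later calendar year. Misclassification further needs a cut-off to be crossed. All of this stands.

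A reader might go further and infer that both subgroup factors are in fact misclassified, that a large share of the adult-onset group is really childhood onset, or that a treatment-by-onset interaction is pulled towards zero. The SAP supports none of these. If AD duration runs from diagnosis, the last branch is correct for it. The falsely adult-onset share depends on the true onset-age distribution, which the SAP does not give. Attenuation of the interaction was not calculated, and it is not guaranteed for the optional three-level split.

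**Conclusion.** The wording error is real and minor. As written, the last branch overstates age at first appearance, and understates time since first appearance, by roughly the appearance-to-diagnosis gap for year-only onset dates outside the birth year with diagnosis in a later calendar year. Participants can then move across the 18-year or optional 12-year onset cut, and across the duration median if duration starts at first appearance. How many would do so cannot be determined from the SAP.

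The consequence is confined to descriptive baseline summaries and one or two of the 19 subgroup entries listed in Section 4.2.6.2, all exploratory. The primary model in Section 4.2.6.1 adjusts for age at screening, eosinophils and baseline IGA, none of which uses these dates. The testing hierarchy in Section 4.1.1 is likewise unaffected.

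**What to change.** Three small edits:

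1. In Section 4.2.2, reword the last branch so that a year-only date outside the birth year becomes 1 January of that date's own recorded year: the appearance year for first appearance, the diagnosis year for diagnosis.
2. In Section 4.2.2, add that any imputed date earlier than the date of birth is set to the date of birth, using the section's existing convention for incomplete birth dates.
3. In Section 4.2.6.2, state which date starts the duration of AD at enrolment.

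The cost is a few words in the SAP and a check, with a small change if needed, of the derivation program. No new data are required.
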